3.2 Study hypothesis

H0: PRO-231 ophthalmic solution has a similar safety and tolerability profile as VIGAMOXI® in clinically healthy subjects.

$$H_0: ST_A = ST_B \text{ o } ST_A - ST_B = 0$$

H1: PRO-231 ophthalmic solution does not have a similar safety and tolerability profile as VIGAMOXI® in clinically healthy subjects.

$$H_1: ST_A \neq ST_B \text{ o } ST_A - ST_B \neq 0$$

Operational definition of similarity: To reject H0, the p-value in the primary variables must be ≤ 0.05 and the 95% CI of this difference must not include zero. Both conditions for hypothesis testing (p-value and 95% CI) must be met, otherwise the result will be interpreted as "**absence of evidence**", not as "**evidence of absence**".

4. Study design

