7.4 Outcome variables

7.4.1 Primary outcome variables

7.4.1.1 Security

- Incidence of unexpected AEs related to interventions.
- Incidence of conjunctival hyperemia and chemosis.
- Changes in the AVMC evaluated with the Snellen chart.
- Changes in ocular surface integrity using fluorescein staining, using the Oxford scale.

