10.1.1 Calculation methodology

Although sample estimation in phase 1 studies is common in treatments whose toxicity/risk is high, as it is in clinical studies for the management/survival of cancer; It was considered pertinent to estimate the sample size according to the safety profile reported in the literature after the use of moxifloxacin hydrochloride. Considering the primary safety variables of the protocol: [59]

- Incidence of AD
- Changes in ophthalmologic signs
- Changes in the AVMC
- Changes in fluorescein staining of the ocular surface

The equation was used to compare two proportions: two samples, two sides of equality. This calculation is useful when you want to test whether the proportions of two groups are different (Incidence of AD in VIGAMOXI® is different from the incidence of AD in PRO-231). The following formulas are used for the calculation to compute the sample size and power respectively: [60]

$$n_A = kn_B \text{ y } n_B = \left(\frac{p_A(1 - p_A)}{k} \right) \left(\frac{z_{1-\alpha/2} + z_{1-\beta}}{p_A - p_B} \right)^2$$

$$1 - \beta = \Phi\left(z - z_{1-\alpha/2}\right) + \Phi\left(-z - z_{1-\alpha/2}\right), z = \frac{p_A - p_B}{\sqrt{\frac{p_A(1-p_A)}{n_A} + \frac{p_B(1-p_B)}{n_B}}}$$

Where:

$k = n_A/n_B$: ratio between the sample sizes of the two groups

Φ : Function of Standard Normal Distribution

Φ^{-1} : The standard normal quantile function

α : error tipo I

β : error tipo II

The proportion of subjects who had at least one AE (ocular and non-ocular) was considered in the study by Garg et al. (2015), where they evaluated the clinical and antibacterial efficacy, as well as the safety of besifloxacin ophthalmic suspension compared to moxifloxacin 0.5% (besifloxacin; n=61, moxifloxacin; n=62). A total of 6 ocular AEs were present in subjects treated with moxifloxacin and at least one AE occurred in 3 patients. The most common AE was conjunctivitis (3.2%). For the expected proportion of subjects of PRO-231, 50% was used, which is a conservative value and gives larger samples. The calculation was made using the free software R (R Core Team, 2021), using a code available online for this purpose. [56] [61] [62]

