10.1.2 Size Calculation

PRO-231 ophthalmic solution is expected to be safe in its ophthalmic application as it presents an incidence of AE similar to that presented by VIGAMOXI.®

On this basis, a sample of 17 ophthalmologically and clinically healthy subjects was estimated. This value increased by 10% considering possible losses. Based on this consideration, 19 subjects per arm (38 subjects in total) are required to provide one eye (OD) to respond to the primary objective of the study.

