10.3.1 Population Analysis

The statistical analysis will be presented to give a general summary of the subjects entered into the study and a view of the safety and tolerability of its results. The data provided by the research site will be summarized for this purpose, according to its nature. The Shapiro-Wilk test will be performed to find out if the quantitative data are distributed in a normal way ($p>0.05$).

The results of the quantitative variables will be presented in measures of central tendency: mean, standard deviation and/or ranges. Changes in the AVMC and ICO will be expressed as continuous variables. Whereas, the incidence (number) of AEs will be expressed as a discrete variable.

The result of the nominal and ordinal qualitative variables will be presented in frequencies, proportions and/or percentages. For these, tables of frequencies $p \times q$ will be constructed. All percentages will be presented with a decimal.

The level of difference to consider significance will be an alpha (α) of 0.05 or less, the 95% CI will be calculated for these differences. The triangulation between the type of variable and the measurements is shown in Table 5. [63]

The operational definition of the study for hypothesis testing will be as follows:

Hypothesis testing	value	Result	Interpretation
P value	≤ 0.05		
95% CI	Does not include zero	H_0 rejected	Both treatments are different in terms of safety and tolerability
P value	≥ 0.05	H_0 accepted	Both treatments are similar in terms of safety and tolerability (they are not different)
95% CI	Includes zero		

Both conditions for hypothesis testing (p-value and 95% CI) must be met, otherwise the result will be interpreted as "**absence of evidence**", not as "**evidence of absence**".

Board 5. Triangulation of concepts.

Variable Type	Variable	A1	A2	B1	C1	C2	C3	C4	D1	E1	F1	F2	F3	F4
Selection														
A1	Demographic			D										
A2	Medical History/Selection Criteria				D									
Basal														
B1	Comprehensive ophthalmological evaluation			T	D	TB	TB	B	T		TB			
Primary Security														
C1	Incidence of unexpected-related AEs				TB					TB				
C2	Incidence of conjunctival hyperemia and chemosis			T		TB				TB				
C3	AVMC			B	TB			B		TB				
C4	Corneal and conjunctival stains with fluorescein			B	TB			B		TB				
Primary Tolerability														
D1	ICO								B					
Secondary Security														
E1	Incidence of AE*			T			TB							
Secondary Tolerability														

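### The assumed 50% adverse event rate on PRO-231 is called conservative, but in the two-sample test used it gives a smaller sample than any lower rate above the reference

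*Combined protocol and SAP*

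**What the plan says.** Section 10.1.1 describes the method: "The equation was used to compare two proportions: two samples, two sides of equality". For the reference arm it uses a published trial of moxifloxacin 0.5%: "The proportion of subjects who had at least one AE (ocular and non-ocular) was considered". From that trial it reports 62 subjects on moxifloxacin, 6 ocular AEs, at least one AE in 3 patients, and conjunctivitis as the most common AE at 3.2%. It does not say which figure was entered. For the test product it states: "For the expected proportion of subjects of PRO-231, 50% was used, which is a conservative value and gives larger samples".

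Section 10.1.2 gives the expectation, "PRO-231 ophthalmic solution is expected to be safe in its ophthalmic application as it presents an incidence of AE similar to that presented by" the comparator, and the result: "a sample of 17 ophthalmologically and clinically healthy subjects was estimated". This is raised by 10% to 19 per arm, 38 in total. No power is stated.

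Section 7.4.1.1 lists "Incidence of unexpected AEs related to interventions" as a primary safety variable. In the decision table of section 10.3.1, a p-value of at least 0.05 with a 95% CI that includes zero means "Both treatments are similar in terms of safety and tolerability (they are not different". The synopsis and section 3.2 first set the conditions for rejecting the null hypothesis and then say "Both conditions for hypothesis testing (p-value and 95% CI) must be met, otherwise the result will be interpreted as" absence of evidence.

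**The concern.** A proportion of 50% maximises p(1 − p), so it is the cautious choice when one proportion is to be estimated to a fixed precision. Section 10.1.1 does something else: it compares two proportions, and the squared difference in the denominator dominates. Setting PRO-231 at 50% against a reference of a few per cent assumes a very large harm, and a very large harm needs few subjects to detect. The stated property is therefore reversed.

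The word used for the 50% is also hard to square with section 10.1.2. A rate of 50% cannot be the expected rate if the incidence is expected to be similar to a comparator at or below about 10%.

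At stake is how a null safety result is read. A committee told that the input was conservative may suppose that the trial can detect moderate differences in AE incidence. The section 10.3.1 table would then turn a non-significant comparison into a finding of similarity, although such a result is likely even with a 25-point excess.

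**Working it through.** **Inputs**

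- Two-sided alpha 0.05 (sections 10.1.1 and 10.3.1); 1:1 allocation (section 7.3).
- PRO-231 rate 50% (section 10.1.1).
- Reference rate, not declared: 3/62 = 4.8% (subjects with at least one AE) or 6/62 = 9.7% (ocular AEs over subjects).
- Power, not declared: 80% and 90% are assumed here.

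**Formula.** Per arm, n = [pA(1 − pA) + pB(1 − pB)] × ((z₀.₉₇₅ + z_power)/(pA − pB))². The sample-size formula in section 10.1.1, as it reads in the text available, shows one variance term, while the power formula beside it shows two. That may be a text-extraction fault, so both terms are used here.

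**The plan's own figure.** With 6/62 versus 0.50 at 80% power, (1.960 + 0.842)² = 7.849, so n = (0.0874 + 0.25) × 7.849 / 0.4032² = 16.29, which rounds up to 17. The loss allowance gives 19 by either method: 17/0.9 = 18.9 and 17 × 1.1 = 18.7. Other inputs also give 17: 3/62 at 92% power (16.44) and 3.2% at 95% power (16.67). The figure is attainable, but its inputs cannot be identified.

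**Effect of the assumed PRO-231 rate (n per arm, 80% / 90% power)**

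| PRO-231 rate | versus 3/62 | versus 6/62 |
|---|---|---|
| 50% | 12 / 16 | 17 / 22 |
| 40% | 19 / 25 | 28 / 38 |
| 30% | 32 / 43 | 57 / 76 |
| 20% | 71 / 95 | 183 / 244 |

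The pattern is general. The derivative of n with respect to pB has the sign of −[pA(3 − 2pA − 2pB) + pB], which is negative for 0 < pA < pB ≤ 0.5. A grid check over all such pairs (step 0.001) found no exception for the unpooled formula, the pooled formula, or the one-term formula with pA read as either arm. Power only rescales n in the unpooled formula.

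**What 17 or 19 per arm can detect.** This is exact binomial power for the any-AE proportion, using Pearson chi-square when all expected counts are at least 5 and Fisher's exact test otherwise (section 10.3.2.1), rejecting at p ≤ 0.05.

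| Comparison | 17 per arm | 19 per arm |
|---|---|---|
| 4.8% vs 50% | 86% | 91% |
| 4.8% vs 40% | 64% | 73% |
| 4.8% vs 30% | 36% | 44% |
| 4.8% vs 20% | 12% | 16% |
| 9.7% vs 50% | 73% | 81% |
| 9.7% vs 30% | 22% | 27% |

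For an excess of exactly 25 points, power is 33% to 36% at 17 per arm and 40% to 44% at 19, depending on the reference.

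At 17 per arm, 80% power is reached at 4.8% versus about 47% or 9.7% versus about 54%, an excess of 42 to 44 points. At 19 per arm the PRO-231 rates are about 43% and 50%, an excess of 38 to 40 points. Also requiring a Wald 95% CI that excludes zero (the plan names no CI method) changes no rejection at either size. The t-test and Mann-Whitney test on AE counts, also listed in Table 2, were not modelled.

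**Primary AE variable.** The documents give no reference rate for unexpected related AEs, so the figures above are not its power. As a best case, with a comparator rate of 0%, 80% power still needs about 36% on PRO-231 at 17 per arm (33% at 19).

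**The case against.** No number in section 10.1 is shown to be wrong: 17 follows from 6/62 versus 50% at 80% power, and 19 follows from 17. The plan applies the word conservative to the 50% input and never to the 38 subjects, and phase I sizes are often pragmatic. All of that is fair, and it is why neither the sample size nor the test needs to change. It does not save the second half of the clause, which is a mathematical statement about sample size and is false.

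The decision table could be called a separate matter. Within section 10.3.1 the absence-of-evidence sentence follows the table and may cover only cases where the p-value and the CI disagree. That reading is possible there. It is not available in the synopsis or section 3.2, which have no row for accepting the null hypothesis and attach the wording to any failure to reject. The conflict with those two places stands.

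Quoting power at 17 per arm alone would be too pessimistic if all 19 are evaluable, and section 5.2.2 allows some replacement of subjects. Against that, the primary analysis is per protocol, which can reduce the number. Both sizes are therefore shown.

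**Conclusion.** The concern holds. For the test that section 10.1.1 names, 50% gives the smallest sample of any PRO-231 rate above the reference and up to 50%. The direction does not depend on which power, reference rate or formula variant was used; the sizes quoted do rest on the assumed power and the two candidate reference rates. Against 6/62 at 80% power, moving the alternative from 50% to 30% raises the need from 17 to 57 per arm. The planned size has 80% power only for an any-AE excess of about 42 to 44 points with 17 evaluable per arm, or 38 to 40 with 19. Separately, 17 cannot be verified until the reference proportion and power are declared, but it is not shown to be an error. This should be corrected, because it bears on what a null AE comparison can be taken to show.

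**What to change.** Keep 38 subjects and revise the text.

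1. In section 10.1.1, delete the clause that calls 50% conservative and says it gives larger samples.
2. Describe 50% as the PRO-231 rate assumed as the alternative for sizing, about 45 points above 3/62 or 40 above 6/62, and not as the expected rate.
3. State the reference proportion entered, the power and the two-sided alpha of 0.05. Check that the printed sample-size formula carries both variance terms.
4. Add the sensitivity. Suggested wording: With 17 evaluable subjects per arm under the chi-square/Fisher rule, 80% power for the any-AE proportion is reached only at about 4.8% versus 47% or 9.7% versus 54%; power is about 36% for 4.8% versus 30% and 12% for 4.8% versus 20%. With 19 evaluable per arm, 80% power is reached at about 43% or 50% on PRO-231.
5. Add that this is not the power for unexpected related AEs, for which no reference rate is available, and give the best-case bound of about 36% versus 0% at 17 per arm.
6. Reconcile the similarity row of the section 10.3.1 table with the synopsis and section 3.2, so that a non-significant AE comparison is not reported as showing similarity.

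The cost is text in section 10.1 and one row of a table, with no extra subjects and no change of test. The sponsor gives up the description of the sizing assumption as conservative.

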10.1.2 Size Calculation

PRO-231 ophthalmic solution is expected to be safe in its ophthalmic application as it presents an incidence of AE similar to that presented by VIGAMOXI.®

On this basis, a sample of 17 ophthalmologically and clinically healthy subjects was estimated. This value increased by 10% considering possible losses. Based on this consideration, 19 subjects per arm (38 subjects in total) are required to provide one eye (OD) to respond to the primary objective of the study.

10.2 Clinical Data Management

The *clinical data management* (or clinical data management, CDM), allows the generation of high-quality, reliable data with statistical value. CDM is the process of collecting, cleaning, and managing the information of the subjects of a study in accordance with regulatory standards (guidelines 21 CFR Part 11, ICH and GCP). It covers the design of the electronic case report form (eCRF), comments on the eCRF, database design, capture (*data entry*), validation (*source document verification*, SDV), discrepancy management (*You want*), medical coding (*medical coding*), extraction (*soft lock*) and database shutdown (*hard lock*). [63]

In accordance with roles and responsibilities, multiple users can be created, whose types of access to the eCRF can be limited to capture (principal investigator, IP), medical coding, database design, or quality control (*quality check*) . The handling of discrepancies will be carried out based on the flow in the [63, 64]Figure 4.

The following roles will be included in the CDM team:

- Data Manager
- Database Designer/Programmer
- Medical Coder
- Clinical Data Coordinator
- Quality Control
- Capturist (*data entry associate*)

[figure not shown]

Figure 4. Handling discrepancies.

(DCF, medical note; CRA, clinical monitor; PI, principal investigator; SEC, self-evident correction) [63]

10.3 Statistical methodology

The statistical analysis plan (PAE) was developed considering the evaluation criteria described in the study protocol.

The statistical analysis will be carried out by personnel of Laboratorios Sophia, S.A. de C.V. Specialized statistical software (SPSS version available [IBM Corporation, Armonk, NY, USA] or R [*The R Foundation for Statistical Computing*; <http://www.R-project.org>]), for Windows. The coding will be done using consecutive numbers. The data will be collected and sorted in an Excel spreadsheet (Microsoft® Office). The data will then be exported to the platform of the selected statistical package. The variables will be categorized according to their nature (see [Board 2](#)). The statistical tests used will be following the corresponding assumptions for parametric statistics as long as the assumption of normality is met (Shapiro-Wilk, $p>0.05$).

10.3.1 Population Analysis

The statistical analysis will be presented to give a general summary of the subjects entered into the study and a view of the safety and tolerability of its results. The data provided by the research site will be summarized for this purpose, according to its nature. The Shapiro-Wilk test will be performed to find out if the quantitative data are distributed in a normal way ($p>0.05$).

The results of the quantitative variables will be presented in measures of central tendency: mean, standard deviation and/or ranges. Changes in the AVMC and ICO will be expressed as continuous variables. Whereas, the incidence (number) of AEs will be expressed as a discrete variable.

The result of the nominal and ordinal qualitative variables will be presented in frequencies, proportions and/or percentages. For these, tables of frequencies $p \times q$ will be constructed. All percentages will be presented with a decimal.

The level of difference to consider significance will be an alpha (α) of 0.05 or less, the 95% CI will be calculated for these differences. The triangulation between the type of variable and the measurements is shown in Table 5. [63]

The operational definition of the study for hypothesis testing will be as follows:

Hypothesis testing	value	Result	Interpretation
P value	≤ 0.05		
95% CI	Does not include zero	H_0 rejected	Both treatments are different in terms of safety and tolerability
P value	≥ 0.05	H_0 accepted	Both treatments are similar in terms of safety and tolerability (they are not different)
95% CI	Includes zero		

Both conditions for hypothesis testing (p-value and 95% CI) must be met, otherwise the result will be interpreted as "**absence of evidence**", not as "**evidence of absence**".

Board 5. Triangulation of concepts.

Variable Type	Variable	A1	A2	B1	C1	C2	C3	C4	D1	E1	F1	F2	F3	F4
Selection														
A1	Demographic			D										
A2	Medical History/Selection Criteria				D									
Basal														
B1	Comprehensive ophthalmological evaluation			T	D	TB	TB	B	T		TB			
Primary Security														
C1	Incidence of unexpected-related AEs				TB					TB				
C2	Incidence of conjunctival hyperemia and chemosis			T		TB				TB				
C3	AVMC			B	TB			B		TB				
C4	Corneal and conjunctival stains with fluorescein			B	TB			B		TB				
Primary Tolerability														
D1	ICO								B					
Secondary Security														
E1	Incidence of AE*			T			TB							
Secondary Tolerability														
F1	Presence of burning								B	TB				
F2	ETS Presence								B		TB			
F3	Presence of pruritus								B		TB			
F4	Presence of tearing								B		TB			

Abbreviations: AVMC, best corrected visual acuity; B, bivariate analysis; D, descriptive statistics; AE, adverse event; ICO, eye comfort index; SCE, foreign body sensation; T, contingency table p x q. *EAs related or not, with the research product.

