7.4.3 Definition of variables, methods and scales for their measurement

Board 2. Operational definition of variables

Variable	Conceptual Definition	Operational Definition	Measurement Type	Reference value	Statistical test
Incidence of Intervention-Related Unexpected AEs	Any adverse medical event that occurs in the clinical research subject to whom any of the interventions were administered and that has a certain coincidental relationship to the interventions [33]	All AEs (according to protocol) in which the PI suspects a causal relationship with the interventions will be reported	• Discrete quantitative • Nominal qualitative	• Relationship with IP • Severity • Causality	
 • Student's t-test of independent groups • U de Mann Whitney* • Pearson X² or Fisher Exact*
Incidence of conjunctival hyperemia	It is the reaction of the conjunctiva to a stimulus, a red appearance secondary to the vasodilation of the conjunctiva vessels of variable intensity is seen	Direct observation. Classification by Efron scale. See attachment 16.2. Efron Scale for Conjunctival Hyperemia	Degrees: 0 = Normal, I = Muy live, II = Mild, III = Moderate and IV = Severe		
 • Pearson X² or Fisher Exact* • McNemar Test*
Incidence of Chemosis	It is defined as conjunctival edema, the result of an inflammatory reaction. It is classified as present or absent	The evaluator will use a narrow beam of light at 60° and will measure whether the conjunctiva separates ≥ 1/3 of the total	• Nominal qualitative	Present / Absent	
 • Pearson X² or Fisher Exact* • McNemar Test*

Variable	Conceptual Definition	Operational Definition	Measurement Type	Reference value	Statistical test
Changes in the AVMC	Visual spatial acuity is the ability to distinguish separate elements of an object and identify them as a whole. It is quantified as the minimum angle of separation (located at the nodal point of the eye) between two objects that allows them to be perceived as separate objects	eyelid opening or if it exceeds the gray line Cartilla de Snellen. Ver anexo 16.5 Fraction to LogMAR conversion table.	• Continuous quantitative	20/30 (0.2 LogMAR) or better	
 • Student's t-test of independent groups • U de Mann Whitney*

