8.5.2.3 Persistent or recurrent adverse events

A persistent adverse event is one that spreads continuously without resolution between different points of assessment of the subject. Such events only need to be registered once in the eCRF. The initial severity (intensity or degree) of the event will be recorded at the time of the first AD record. If a persistent AE becomes acute, the maximum severity should be recorded in the appropriate section of the eCRF. If the event becomes a serious event, it must be reported no later than 24 hours after the knowledge of the change in the status of the event. The eCRF section should be updated to reflect the serious status, and will record the date on which the event became serious, thus completing all relevant serious EA reporting data.

A recurrent AE is one that resolves between assessment points and subsequently reappears. Each recurrence of the EA must be recorded separately in the eCRF.

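### Adverse event incidence is sized as a per-subject proportion but analysed as a number of events, and the plan never says which form of the variable decides the primary comparison

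*Combined protocol and SAP*

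**What the plan says.** All references are to the combined protocol and SAP.

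- **Sizing (Section 10.1.1).** "The equation was used to compare two proportions: two samples, two sides of equality". The input is per subject: "The proportion of subjects who had at least one AE (ocular and non-ocular) was considered". On the comparator side the cited trial is summarised as "A total of 6 ocular AEs were present in subjects treated with moxifloxacin and at least one AE occurred in 3 patients", out of 62. On the other side, "For the expected proportion of subjects of PRO-231, 50% was used".
- **Analysis form (Section 10.3.1).** "the incidence (number) of AEs will be expressed as a discrete variable".
- **Table 2 (Section 7.4.3).** Unexpected related AEs, the first primary variable, are typed as discrete quantitative and also as nominal qualitative. The tests are "Student's t-test of independent groups", "U de Mann Whitney" and Pearson chi-square or Fisher. The last two carry a footnote limiting them to cases where they apply. The secondary AE row has the same types and tests.
- **Choosing a test (Section 10.3.2.1).** Quantitative variables go to Student's t if Shapiro-Wilk is passed in each group, otherwise to Mann-Whitney. Qualitative variables go to chi-square, or to Fisher when expected values are below 5.
- **Recording (Section 8.5.2.3).** "Each recurrence of the EA must be recorded separately in the eCRF".
- **Decision rule (Sections 3.2 and 10.3.1).** H0 is rejected when p is at most 0.05 and the 95% interval excludes zero. The rule names neither the test nor the interval method.

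**The concern.** A number of events and a proportion of subjects are different quantities. Because each recurrence is a separate record, a count mixes how many subjects react with how often one subject reacts. The sizing calculation concerns only the former.

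Table 2 admits both forms, so two analyses of the first primary variable are legitimate under the plan. Each has its own p-value, and the decision rule does not say which one counts. If they fall on opposite sides of 0.05, the choice could be made after the data are seen, between calling the products different and calling them similar or the evidence inconclusive.

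**Working it through.** **1. The plan's own figure.** Section 10.1.2 gives 17 per arm, raised by 10% to 19. The formula as printed lacks the second variance term. The usual unpooled form is n = [pA(1−pA) + pB(1−pB)] × [(z₀.₉₇₅ + z_power)/(pA − pB)]². Power is not stated; 80% is assumed first, so z₀.₉₇₅ + z_power = 2.802.

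- pA = 6/62 = 0.0968, pB = 0.50: (0.0874 + 0.25) × (2.802/0.4032)² = 16.29, so 17.
- pA = 3/62 = 0.0484, pB = 0.50: (0.0460 + 0.25) × (2.802/0.4516)² = 11.39, so 12. At 90% power it is 15.25, so 16.
- 17 × 1.10 = 18.7, so 19.

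The stated 17 is therefore reproduced, and under either input the calculation concerns a binary outcome per subject.

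**2. Which tests remain in play.** With sparse counts Shapiro-Wilk fails decisively: 4 events among 19 subjects gives p below 0.00001. In an arm with no AEs the data are constant and the test is undefined. The quantitative route therefore leads to Mann-Whitney, and the qualitative route to chi-square or Fisher.

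**3. Illustrative data under the plan's rules** (two-sided; Mann-Whitney by normal approximation with continuity correction; chi-square uncorrected).

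| Data | Per arm | Quantitative route | Qualitative route |
|---|---|---|---|
| 4 vs 0 subjects, 1 AE each | 19 | Mann-Whitney 0.040 | Fisher 0.105 (expected 2) |
| same | 17 | 0.039 | 0.103 |
| 3 subjects with 2 AEs each vs 9 with 1 each | 19 | Mann-Whitney 0.124 | Chi-square 0.036 (expected 6) |
| same | 17 | 0.131 | 0.031 |

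**4. Why they differ.** In the first case the data are 0/1 either way. A permutation version of Mann-Whitney gives about 0.10, in line with Fisher, so the gap is asymptotic versus exact. In the second case the count itself matters. At 19 per arm, 3 versus 9 subjects with one AE each gives Mann-Whitney p = 0.041; giving each of the three a second AE moves the same test to 0.124, although the same subjects reacted.

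**5. Effect on the two-condition rule, second case, 19 per arm.**

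- Proportions: 9/19 − 3/19 = 0.316. The standard error is √(0.1579×0.8421/19 + 0.4737×0.5263/19) = 0.142, and the Wald interval is 0.316 ± 1.96×0.142 = 0.04 to 0.59. With p = 0.036, H0 is rejected.
- Counts: mean difference 9/19 − 6/19 = 0.158, t-based interval −0.265 to 0.580. With p = 0.124, H0 is not rejected.

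**6. How often.** At 19 per arm, with one AE per affected subject, Mann-Whitney and the chi-square/Fisher rule disagree in 0.9% of trials if both rates are 5%, in about 2% at 4.8% versus 50%, and in about 14% at 4.8% versus 25%. Simulated counts averaging 2 AEs per affected subject give 13% at 4.8% versus 25%.

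**The case against.** **The plan does have test-selection rules.** This is right, and it would be wrong to say that nothing governs the choice. Section 10.3.2.1 settles t versus Mann-Whitney and chi-square versus Fisher. It does not settle which pair governs a variable that Table 2 puts in both classes. Table 5 codes the variable for contingency tables and bivariate analysis, which does not settle it either.

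**A reader might infer that a t-test will be run on near-zero counts.** Table 2 lists it, but the normality check removes it in practice, so t-test p-values are not evidence against this plan.

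**A reader might infer that the routes generally conflict.** They usually agree. With 5 versus 0 of 17, one of the five having 6 events, Mann-Whitney gives 0.019 and Fisher 0.044: both reject. The second example in the table also depends on the plan's use of uncorrected chi-square, since Fisher on the same data gives 0.079.

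**Chi-square/Fisher may be meant only for severity or causality categories.** Then the proportion used for sizing has no named test, and the mismatch remains.

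**A reader might infer that events were entered as subjects in the sample size.** 6/62 reproduces 17 at 80% power, but power is not stated, and 3/62 at 90% power gives 16. The documents do not establish which was used.

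**A reader might infer that the trial is sized on this primary variable.** It is not. Section 10.1.1 uses any AE, ocular or non-ocular, while the primary variable is unexpected related AEs. The link is to the form, a per-subject proportion, and not to the AE class.

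**Conclusion.** The point holds and the text is wrong as written. Sizing uses a per-subject proportion, Section 10.3.1 prescribes a number of events, and no section says which result decides.

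The p-value can cross 0.05 in either direction (0.040 versus 0.105; 0.124 versus 0.036). Disagreement occurred in about 1% to 14% of trials in the scenarios tried. Those frequencies rest on assumed event rates, 19 analysed per arm and asymptotic Mann-Whitney, whose version the plan does not specify. The inconsistency in the text rests on none of these assumptions.

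**What to change.** In both AE rows of Table 2 and in Section 10.3.1:

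- Define AE incidence as the number and proportion of subjects with at least one AE of the stated class.
- Name Fisher's exact test as the only deciding test, and remove Student's t and Mann-Whitney.
- Name an exact 95% interval for the risk difference that is consistent with that test. This matters: for 4/19 versus 0/19 the Wald interval is 0.2105 ± 1.96 × √(0.2105×0.7895/19) = 0.03 to 0.39, which excludes zero while Fisher gives 0.105. Not every exact interval agrees with Fisher, so check agreement over all 20 × 20 = 400 possible tables at 19 per arm before fixing the method.
- Report event counts and recurrences descriptively.

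The cost is SAP wording; visits, data collection and sample size are unchanged. The downside is that Fisher's test is conservative here. At 19 per arm its type I error is 0.1% with both rates at 4.8% and 1.0% with both at 9.7%. Its power against 50% is 87.6% if the comparator rate is 3/62 and 71.9% if it is 6/62. Because Section 10.3.1 reads non-rejection as similarity, the interval should always be shown beside the p-value.
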